2.5 PARTICIPANT WITHDRAWAL

2.5.1 Dropout Definition

If a participant declares he/she is no longer interested in completing the study, he/she will be considered a "dropout." Once given "dropout" status, the participant can no longer contribute to the study.

2.5.2 Dropout Compensation

If participant decides to stop participating in the study prior to starting the inpatient portion of the study, he/she will only receive compensation for the Screening Visit (\$30) and no compensation will be given for the inpatient portion.

If a participant decides to drop out during the inpatient study, compensation will be pro-rated for completed visits.

2.5.3 Lost to Follow-Up

If a participant is unable to be contacted and does not respond to calls from the Clinical Research Coordinator, he/she will be considered "lost to follow-up" (LTFU). If a participant is considered LTFU, every effort will be made to contact him/her.

2.5.3.a Contact Attempts

After three unsuccessful phone and email contact attempts, a letter of intent to contact will be mailed to the participant's home address. This letter will inform the participant that they will be formally withdrawn from the study by the date that is 90 days past the last point of contact. It will also include details on the remaining study compensation available if procedures were continued. If the participant fails to contact the CRC after this outreach, and 90 days have passed

Short-Term Cardiovascular Effects of E-Cigarettes: Influence of Device Power IRB# 17-23965
since last communication, he/she will be considered “lost to follow-up”. No further outreach will be conducted. Once given “LTFU” status, the participant can no longer contribute to the study.

2.5.3.b Returning to Visit Procedures

[figure not shown]
If a formerly lost participant returns, before starting the inpatient portion of the study, the reassessment of eligibility steps outlined in Section 2.3.4 of this manual will be followed. If the participant is LTFU during some point in his/her inpatient portion, there will not be the option to repeat this.

3 STUDY DESIGN

3.1 VISIT SCHEDULE

The study will consist of 3 Study Arms, for 2 outpatient hospital days each.

The Study Visit chart below describes the schedule of visits and procedures.

3.2 SCHEDULE OF ASSESSMENTS

3.2.1 Visit Windows

Table 1 describes the schedule of visits in relation to the start point of the Phone/Email Screen. Ideally, participant assessments will fall within the designated windows.

Table 1

Assessment Point	Maximum Time allowed from Phone/Email Screen	Maximum Time allowed from Screening Visit

Phone/Email Screen		
Screening Visit	30 days	
Orientation	120 days	90 days

Every effort should be made to enroll and run eligible participants. Thus, if participants are outside of their screening visit or orientation visit windows, reassessment of eligibility will occur as described in Section 2.3.4.

4 RECRUITMENT METHODS

Our methods of recruitment will be as follows:

- Postings to craigslist (paid and free sections)
- Flyers posted in mostly institutional settings (colleges, career centers, churches) and left at vape and smoke shops
- Newspaper ads (typically Bay Guardian, SF Weekly, East Bay Express)
- Blogs, google+ and social networking sites (e.g., Facebook, Reddit, etc)
- Contact of prior callers or study participants who have given permission for re-contact as documented either in the consent form for the prior study or in our phone screening database.

Individuals who respond to recruitment postings/flyers will be screened initially by REDCap survey to determine potential eligibility. Based on this initial assessment they may be asked to come to the UCSF Tobacco Research Center for an in-person screening visit. Additionally, participants from previous studies at the UCSF Tobacco Research Center, who appear to be eligible for the study will be re-contacted and asked if they are interested in participating.

4.1 PRELIMINARY REDCAP SCREENING

Individuals who see the ad will be prompted to click on a hyperlink which will lead them to a preliminary screen on REDCap, or email the UCSF Tobacco Coordinator email address for more information.

The preliminary REDCap screen is a short survey in which the participants provide the following information:

- Contact information
- E-Cigarette/Tobacco Cigarette product use
- Prescription Medication Use
- Exclusionary medical conditions

This REDCap survey is programmed to generate a report of eligible participants. The information for eligible participants will be exported weekly from REDCap into an Excel sheet. The CRC will use this information to call only valid prospects to complete a comprehensive confidential phone screen.

Eligible participants may be contacted by phone or email if any follow-up clarification questions are needed.

Eligible participants will be screened over the phone and the CRC will obtain e-consent via DocuSign or another electronic signing system. The participant will then come in for an in-person screening visit to complete the Medical History form and sign the HIPAA form. The CRC will send two separate emails containing the consent form and PowerPoint Summary and then another email containing the REDCap survey link. The participant will be given 3 available appointment options from which they may choose to come in for an in-person screening visit. Participants will then respond with their desired appointment option, and will be scheduled for an in-person

The participants may choose to sign the consent form in person if they have trouble with the e-consent process.

4.2 PHONE EVALUATION & E-CONSENT (SCRIPT)

Individuals who are preliminarily eligible based on results from the Online Screening will be contacted for a phone evaluation to further determine eligibility prior to scheduling an in-person Screening Visit.

The procedures for the e-consent are as follows:

- CRC and participant engage in consent discussion over the phone. During this discussion CRC will review purpose, procedures, risks/benefits and alternatives. CRC will ask questions to assess the understanding of the participant.
- Participant is sent the consent powerpoint to review via email
- Participant is sent the consent form to sign in Docusign (after signing, CRC will immediately sign in Docusign and download e-consent to save on study server)
- The CRC will update the participant enrollment log assigning them a Study ID.
- Approximately 24-hours before coming in for the study visit, participant is sent the screening packet to complete online via REDCap.
 - In REDCap, CRC will add new record, assign the study ID and send the survey link directly from the REDCap system
- At the screening visit, participant signs one wet copy of the consent form (to be given to 5B research ward)
- At the screening visit, participant signs 2 HIPPA forms; one for research ward 5B and one for the study team
- At the screening visit, participant will be presented with the Bill of Rights
- Participant will also be presented with the vaping safety handout.

The script for the phone evaluation is as follows:

Phone Evaluation Scripts

Various items related to eligibility must be confirmed by the CRC during a phone conversation.

ALL participants will be asked, *“Are you willing to use a mod e-cigarette for this study?”*

ALL participants will be asked *“Are you allergic to propylene glycol or vegetable glycerin?”*

These following questions will also be asked ***if applicable:***

If participants indicate they are in a drug treatment program, *“I saw you indicated that you are in a drug treatment program. Can you let me know what that is for?”*

OR

“I see that you have listed [methadone] [buprenorphine] as current medications. Can you let me know what that is for?”

If participant uses other tobacco products, *“As part of this study we will ask you to*

avoid other tobacco products like cigarillos, blunts, etc. from the time before your hospital visit through the end of the study period. Are you okay with avoiding these for this amount of time?"

If participant uses marijuana, *"As a part of this study we will ask you to avoid marijuana use from the time before your hospital visit through the end of the study period. Are you okay with avoiding marijuana for this amount of time?"*

If still eligible after those questions, the CRC will schedule the participant for a screening visit. If preliminarily eligible based on the REDCap report, contact the participant by phone and ask the following questions using the script:

Study Team: *"Good afternoon, may I please speak with [name]?"*

If the person is not available: leave a voicemail or thank the person who answered and say goodbye.

If the person is available: First confirm that you are speaking to the correct person.

Study Team: *"This is [name] calling from the UCSF Tobacco Research Center. I am a coordinator working with [name] research group.*

Is this an Ok time for you to speak?"

If the person says "No" or "I'm not sure"

Study Team: *"Okay. [Ask if you can schedule another time to talk. If the person is not sure or seems hesitant, thank him/her and say goodbye.]"*

If the person says "Yes"

Study Team: *"Great. I wanted to talk with you about a study researching the effects of the battery power in e-cigarettes. You may remember you filled out a questionnaire online to be considered for this study. You indicated that you were interested in learning more."*

If the person says "No" or "I'm not sure"

Study Team: *"No problem. I just wanted to make sure you had the opportunity to learn about any study we have at the UCSF Tobacco Research Center. Thank you for your time."*

If the person says "Yes"

Study Team: *"We are conducting this research study to look at the effects of battery power in e-cigarettes. We want to know more about how vaping at low, medium, and high power levels changes how the body is exposed to nicotine and what effects the e-cigarette has on the heart. Just so you know in advance, if you choose to participate in the study, it will take place at San Francisco General Hospital for three study "arms, which include two consecutive hospital days each "arm", you will be using e-cigarette products that we will provide and filling out questionnaires. There will be blood draws, we will be measuring your blood pressure and heart rate, as well as collecting urine samples. You will also be provided with meals during your stay, and the research rooms at SF General have free Wi-Fi and TVs with cable. Do you have any questions so far?"*

If you are still interested, the first step is for me to ask you some questions to see if you are a good match for the study. This can take about 20 minutes. Do you have the time right now to speak with me? Do I have your consent to ask these questions?"

Update the Eligibility Checklist as you ask the questions.

Study Team: (If no) *"Okay, well it seems like this study may not be the best fit for you, which is totally fine. Would you like us to keep your name down for other studies as they come up?"*

(If yes, continue)

Study Team: *"Okay, so we reviewed the purpose and procedures of this study. I'd like to let you know that research is 100% voluntary and you can choose at any time to not participate."*

"I'd like to review some risks with you:

Venipuncture and catheterization: *A catheter (small plastic tube) will be placed in a vein in one forearm in order to make it easier to take the multiple blood samples. The catheter will remain in*

Short-Term Cardiovascular Effects of E-Cigarettes: Influence of Device Power
place for about 10 hours. There is a small risk of pain, swelling, bruising, or infections at the blood draw site. IRB# 17-23965

Blood Loss: You will lose a total of about 1 cup of blood during the entire study. This amount of blood loss poses no risk to healthy individuals.

The **Study Procedures** may be inconvenient and tedious (filling out forms, spending time in the hospital, providing specimens, etc.)

You may also feel uncomfortable when getting your **blood pressure** taken depending on the tightness of the cuff.

During **abstinence**, you may feel **uncomfortable, irritable, and restless or have difficulty concentrating** due to possible nicotine withdrawal. This may result in **headaches, nausea, fatigue, or changes in mood**.

Although long-term effects are uncertain, the use of **e-cigarettes could increase dependence on e-cigarettes** as well as pose threats to the pulmonary and cardiovascular systems; exposure to **e-cigarette aerosols can increase risks of cancer and adverse reproductive outcomes**.

Survey Questionnaires: You will be asked to answer **personal and private questions** during this study, including questions about your **medical history, drug and alcohol use, breath sample measurements, urine tests of drug and pregnancy, and questionnaires about your mood**.

Answering these personal questions could make you feel uncomfortable.

And finally, we will be collecting personal information from you, so there is a risk of break of confidentiality. However, we will do our best to keep your confidentiality.

Can I answer any questions about risks?

Okay, let's talk about the benefits. There are no direct benefits to you, but you will be helping us learn about how vaping at low, medium, and high power levels changes how the body is exposed to nicotine and what effects the e-cigarette has on the heart. Which has great potential benefits to other vapers like you. We will also be reimbursing you for your time and effort – if you complete all parts of the study, you will be paid for each study visit and be given a completion bonus. If you complete all parts of the study, you'll get up to \$1,890 for your time and effort. Most of your payment will be processed at the very end.

Can I answer any other questions you might have? (If yes, answer) (If no, proceed)

Okay, can I ask you a few questions?

Do you remember – how long does this study last? (6 total outpatient hospital study days. 8 days total including Screening Visit and Orientation)

Do you remember – how many days will you be expected to stay at the hospital? (6 days total; 2 consecutive outpatient days per Study Arm)

What are some risks you may experience? (Discomfort, bruising, mood changes, breach of confidentiality)

Do you think you are interested in seeing if you are a match for the study?

(If yes) "Great! I am going to send you a PowerPoint presentation via your email. Please look it over – it describes in great detail more information about the study. I will also send you the consent form – please take time to read it over and review carefully. If you agree to participate, you will be prompted to sign the form electronically."

I can schedule you for the next phase of screening – this is a 45 minute screening visit. When would be a good time for you to come in for that?

(Proceed with scheduling visit)

Okay, very important before you come in...

After you sign the consent form and about 24 hours before your visit, I will send you a survey link to your email. It's important that you complete this survey before you come in, otherwise you will need to complete it in person and the visit will take longer than 45 minutes.

At the screening visit we will first review a HIPAA form. This is another important form for you to

Short-Term Cardiovascular Effects of E-Cigarettes: Influence of Device Power
IRB# 17-23965
sign related to the study and your health information privacy. We will then have you fill out a medical history form and we will conduct a quick interview and collect your basic vitals and a saliva sample. At this visit, you will also need to provide a urine sample for a drug test and a pregnancy test, if applicable. A drug test that is positive for any drugs other than marijuana will result in an automatic dismissal without payment. If you pass these tests and complete the screening visit we will compensate you with a \$30 check, which will reach your home within 4-6 weeks.

For this visit, please bring in a valid photo ID to verify your name and age. If you are currently taking any medications, please bring the bottle or a copy of your prescription, so we can verify any medications you are taking. If you need to reschedule your study visit, we will give you one option to reschedule, so please make sure you pick a time that works with your schedule.

Any other questions?

(If no) Great! I will send you two emails, a confirmation email which will include the PowerPoint summary, and another email with the consent form. After signing the consent form and 24 hours before your scheduled visit, I will send you another email with the REDCap survey link prior to your screening visit. Please do not hesitate to contact me with any questions.

5 STUDY VISITS AND PROCEDURES

5.1 SCREENING VISIT

Participants will undergo a 45 minute in-person screening visit to determine study eligibility. During this visit, participants will complete a basic physical assessment: height, weight, heart rate, blood pressure, expired carbon monoxide, urine toxicology test, and pregnancy test (if applicable), saliva collection, and a Screening Packet containing questions regarding medical history and product use.

The schedule of procedures for the screening visit will occur in the order as follows:

5.1.1 Urine Collection

After consent, the participant will be asked to provide a urine collection to test for drug use and pregnancy testing (if female).

If the participant has a positive toxicology screen (marijuana is okay), he/she will be dismissed and given the option to rescreen within 30 days.

5.1.2 Vital Assessment

The following physiological measures will be assessed:

- Height and Weight
- Blood pressure and heart rate

If the participant's blood pressure is out of range, it will be re-tested at the end of the visit manually, following the saliva collection. If it is still out of range, they will be considered ineligible.

5.1.3 Screening Packet

- **Section 1: Personal Data Form (Page 1)**
 - This section contains the participant's contact information as well as an Emergency Contact.
- **Section 4: Medical History (Pages 23-28)**
 - This section contains information regarding the participant's medical history, including exclusionary medical and psychiatric conditions.
 - If any symptoms are endorsed on the Medical History in Section 8, the CRC will follow up with the participant asking:
 - How often and when was the last time you experienced these symptoms?
 - Do you ever take medication for this? If so, how often?

Notes on the Medical History follow-up will be recorded at the bottom of the last page of the form (page 16).

5.1.4 Saliva Collection

After the participant completes the Screening Packet, he/she will be asked to provide a saliva collection.

5.1.5 End of Screening Visit

At the end of the screening visit, the participant will be asked to fill out a "Certificate of Participation" in order to receive compensation for the screening visit. The participant will be dismissed and the CRC will inform him/her that he/she will be contacted in 1-2 weeks with eligibility results from the screening visit.

5.1.6 Post-Processing

The participant's urine will be discarded and the CRC will store the participant's saliva in the freezer at the UCSF Tobacco Research Center lab. The saliva samples will be labeled with the Study ID and transferred to the [name] Lab at the end of the day on Friday afternoons. The CRC will complete a Screening Log on the Shared Lab Drive filling in information on the samples dropped off. Cotinine results will be expected the following Tuesday.

The CRC will complete the Screening Visit Log and enter data from the Screening Packet into the "TCORS-Study 1 Screening Packet" REDCap database. Data entry should occur within 48 hours of the screening visit.

The CRC will submit the participant's check request after confirming the participant's vaping status ($COT \geq 30 \text{ ng/ml}$). If the participant's cotinine is $< 30 \text{ ng/ml}$, they will not be compensated for their screening visit.

5.2 PREPARATION FOR OUTPATIENT PORTION

5.2.1 5B SETUP PAPERWORK

After study dates have been confirmed with the participant and the research ward, a outpatient request will be submitted via secure email to the research ward. The CRC will then prepare CTSI-5B Set-up paperwork for the admissions.

The set-up paperwork consists of the following:

5.2.1.a Coversheet

- The coversheet contains general information regarding the study and supplies needed.
- CRC will place a label with the participant's name and study ID, and edit the admission and set-up drop-off dates.

5.2.1.b Consent Form

- An original signed copy of the consent form from the Screening Visit will be included in the set-up.

5.2.1.c Nurses Flow Sheet

- The Nurses Flow Sheet contains study procedures and time points for each day of the inpatient admission.
- CRC will update this form with participant's device power level assignment.

5.2.1.d Outpatient Form

- The outpatient form has PHI filled out by the participant at the screening visit with name, SSN, date of birth, and contact information.

5.2.1.e MD Orders

- The MD Orders are pre-signed by the Study Physician.
- CRC will write in the admission date and pencil in the participant's name on the top right corner.

5.2.1.f Adverse Event Form

- The Adverse Event form is included in the set-up should any adverse events occur during the course of the study.
- CRC will change the study ID.

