1.2 SPECIFIC AIMS

1.2.1 Specific Aim #1

Determine the impact of e-cigarette device power on nicotine pharmacology, systemic exposure to toxic volatile organic compounds (VOCs), and short-term cardiovascular effects.

Hypothesis 1a: Systemic nicotine exposure and subjective measures of sensation in the throat, reward, and satisfaction will increase with increasing power.

Hypothesis 1b: Mercapturic acid metabolites of VOCs, particularly acrolein, will increase with e-cigarette power.

Hypothesis 1c: CV effects increase with higher power, and are manifested as changes in hemodynamic parameters, hormonal release, and biomarkers of endothelial function, platelet activation, inflammation, and oxidative stress.

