2.4.2 Randomization

Participants will be assigned to begin procedures starting with one of three possible power levels using a Latin square design.

1) 10 Watts

OR

2) 15 Watts

OR

3) 20 Watts

Orientation # (N= 21)	Sequence	Study ARM 1	Study ARM 2	Study ARM 3
1	1	10W	15W	20W
2	2	15W	20W	10W
3	3	20W	10W	15W
4	4	20W	15W	10W
5	5	10W	20W	15W
6	6	15W	10W	20W
7	1	10W	15W	20W
8	2	15W	20W	10W
9	3	20W	10W	15W
10	4	20W	15W	10W
11	5	10W	20W	15W
12	6	15W	10W	20W
13	1	10W	15W	20W
14	2	15W	20W	10W
15	3	20W	10W	15W
16	4	20W	15W	10W
17	5	10W	20W	15W
18	6	15W	10W	20W
19	1	10W	15W	20W
20	2	15W	20W	10W
21	3	20W	10W	15W
22	4	20W	15W	10W
23	5	10W	20W	15W
24	6	15W	10W	20W

The participant will not be considered for assignment until it has been verified that he/she is eligible and the Eligibility Checklist has been signed. The experimental design includes a counter-balanced randomized treatment order to complete replication with total sample sizes of 21 or 24 (complete Blocks of n= 3). At the orientation visit, the participant will be assigned their treatment sequence from the above randomization schedule. In cases where a block will be incomplete because a participant has dropped out or been lost to follow up, their orientation assignment can be reused.

The final order assignment will take place at the orientation visit when the participant is physically present at the UCSF Tobacco Research Center. The CRC will refer to the "Assignment Tracking Log," input the participant's initials, product assignment, and date he/she is assigned to that condition. Assignment does not necessarily reflect the sequence of the participant's consent in the study, but rather when he/she is booked for the start of orientation. That time course will vary based upon participant, CRC and CTSI availability.

If a participant drops out or is lost to follow-up (LTFU) during the study, he/she will not be replaced. The assignment schedule will continue as assigned, and the PI can decide to enroll additional participants to compensate for non-completers.

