5.3.1 Product Assignment

Three e-cigarette device power levels will be assigned to all participants: low, medium, and high battery levels (10, 15, 20 Watts). The order of the assignment will be randomized, single-blinded.

E-liquid Selection: We will obtain the e-liquid from AVAIL, a leading premium e-liquid manufacturer and retail business which works with academic centers to provide research grade products that come with certificates of analysis confirming nicotine content, lack of diacetyl (<38 ppm) and acetyl propionyl (<100 ppm). We will purchase the most popular e-liquid from AVAIL at the time of the study and will contain 12 mg/mL.

E-cigarette Device: The study device is a variable wattage all-in-one device, which is inclusive of the three power levels we intend to study. It is important to note that e-

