5.4.4 PARTICIPANT SCHEDULE

Study Arm #1: Power level 10, 15, or 20 watts (computer randomized, single-blinded)	
Hospital Day 1	Hospital Day 2

• Standardized Session• 4-hr abstinence and blood draws• Followed by 90 min Free use session w/ video monitoring	
• Free use• 12-hr CV monitoring• Circadian blood draws• 12-hr urine collection
Study Arm #2: 1 of the other 2 remaining power levels (computer randomized, single-blinded)	
Hospital Day 1	Hospital Day 2

• Standardized Session• 4-hr abstinence and blood draws• Followed by 90 min Free use session w/ video monitoring	
• Free use• 12-hr CV monitoring• Circadian blood draws• 12-hr urine collection
Study Arm #3: Remaining power level (computer randomized, single-blinded)	
Hospital Day 1	Hospital Day 2

• Standardized Session• 4-hr abstinence and blood draws• Followed by 90 min Free use session w/ video monitoring	
• Free use• 12-hr CV monitoring• Circadian blood draws• 12-hr urine collection

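### The assigned wattage is written on the ward nurses' flow sheet in a study labelled single-blinded: an avoidable, minor risk of cueing that an arm code would reduce

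*Protocol*

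**What the plan says.** On blinding, Protocol 5.3.1 (Product Assignment) has one sentence: "The order of the assignment will be randomized, single-blinded". The participant schedule in 5.4.4 repeats the label for each arm, the first entry reading "Power level 10, 15, or 20 watts (computer randomized, single-blinded". Neither place says who is blinded.

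On paperwork, 5.2.1.c describes the ward document: "The Nurses Flow Sheet contains study procedures and time points for each day of the inpatient admission". The next instruction is "CRC will update this form with participant's device power level assignment".

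On assignment, 2.4.2 (Randomization) states: "The final order assignment will take place at the orientation visit when the participant is physically present at the UCSF Tobacco Research Center". The clinical research coordinator (CRC) then opens the Assignment Tracking Log to "input the participant's initials, product assignment, and date he/she is assigned to that condition".

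On staff, 8.5 gives the CRC the conduct of study visit procedures, and 6.1 has the CRC and the nurses monitor participants during the stay.

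On outcomes, Hypothesis 1a in 1.2.1 is directional and partly self-reported: "subjective measures of sensation in the throat, reward, and satisfaction will increase with increasing power". The phone script in 4.2 tells every candidate that low, medium and high power are being compared.

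**The concern.** The masked variable is written, by instruction, on a sheet intended for the ward where the person presumably masked spends six study days. The text shown describes no code, no covered field and no other concealment step. A nurse who knows the power may give it away in conversation, or the sheet may be left in view.

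The ratings are where this could matter. Each participant rates all three powers, so learning the wattage acts directly on the within-person contrast. Participants know that power is the factor under study, and Hypothesis 1a predicts higher ratings at higher power. An expectation effect would therefore tend to run in the hypothesised direction. A second, smaller route is staff behaviour: how firmly the 4-second puffs of the standardized session are enforced, and how puffs are timed from video, if those doing so know the power.

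**Working it through.** The protocol gives no figure on blinding, so there is none to reproduce. The check is to set the sections side by side.

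1. **Does staff knowledge conflict with the stated blind?** 5.3.1 and 5.4.4 say single-blinded and no more. On the usual reading the participant is blinded and staff are not. No section promises blinded nurses, coordinators or coders. There is no conflict.

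2. **Is the wattage disclosed to the participant at orientation?** 2.4.2 places the participant at the research center when the order is assigned. That fixes when assignment happens (on attendance, not at consent). It does not say that the log is opened in front of the participant or that the order is read out. Disclosure is possible but not stated.

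3. **Does the flow sheet need the wattage?** Sections 5.4.1 to 5.4.3 give the same puff regimen (one 4-second puff every 30 seconds, 10 puffs) and the same heart-rate times in every arm. The blood-draw times also agree wherever they are fully legible. The timed content therefore does not depend on power. But the sheet also lists procedures, one of which is vaping at the assigned power, and the protocol does not say who sets the device. Someone at the visit needs the setting; whether that is a nurse using this sheet is not known.

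4. **Which outcomes are open to cueing?** Withdrawal, craving and reward are rated before and after the sessions on day 1 and four times on day 2. Puffing is paced on day 1 and, in the 90-minute session, measured from video. Blood nicotine, the urine and plasma biomarkers and the ambulatory recordings come from a laboratory or a recorder.

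5. **How large could the effect be?** The document gives no expectancy effect, no within-subject SD and no probability that a participant learns the wattage. For orientation only, assume that no true difference exists and that unblinding shifts a rating by 0.2, 0.3 or 0.5 within-subject SD between two powers. For n completers in the three-period crossover:
   - standard error of a pairwise difference = sqrt(2/n) SD: sqrt(2/21) = 0.309 and sqrt(2/24) = 0.289;
   - residual degrees of freedom = 2(n − 1) − 2: 38 and 44;
   - non-centrality = shift / standard error: 0.648, 0.972 and 1.620 for n = 21; 0.693, 1.039 and 1.732 for n = 24;
   - rejection rate of a two-sided 5% t test (non-central t):

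| Assumed shift (SD) | n = 21 | n = 24 |
|---|---|---|
| 0.2 | 9.7% | 10.4% |
| 0.3 | 15.8% | 17.4% |
| 0.5 | 35.2% | 39.5% |

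The sample sizes are those in 2.4.2; the shifts and the 5% test are assumptions. The table shows what a shift of that size would do to one rating. It does not show that the flow sheet produces such a shift.

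**The case against.** A reader might infer that the protocol breaks its own blind. It does not. Single-blind is compatible with informed staff, and no section shows the participant seeing the sheet or the log. Nor can one conclude that the order is assigned in the participant's sight: 2.4.2 says present at the center, not in the room where the log is kept.

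A reader might also infer that the wattage is on the sheet needlessly. That is not established, because whoever sets the device needs the power and the protocol does not say who that is. The device paragraph in 5.3.1 breaks off in the text available, so any masking of the display may be described there and cannot be counted as missing.

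The benefit of a change is also limited. The CRC holds the log and conducts visits. Participants are experienced users who may sense the power, since Hypothesis 1a itself predicts more throat sensation as power rises. The protocol does not say that nurses administer the questionnaires, pace the puffs or code the videos. The one labelling rule shown, for screening saliva (5.1.6), already uses the Study ID.

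All of this stands, and it lowers the point to minor. It does not remove it: the instruction in 5.2.1.c is explicit, no safeguard accompanies it in the text shown, and whoever sets the device can be given the wattage by other means.

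**Conclusion.** The point holds as a cheap improvement of minor severity. A study labelled single-blinded, with the blinded party unnamed, has the assigned power written on the ward's working sheet while participants there give directional, self-reported ratings. That is an avoidable risk of cueing or accidental disclosure, not a demonstrated breach and not an internal contradiction.

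The risk is confined mainly to the ratings in Hypothesis 1a and to puffing that staff pace or code. Systemic nicotine, the VOC metabolites and the laboratory or recorder-based cardiovascular measures are much less exposed to it.

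Its size cannot be derived from the document. The rejection rates tabulated in the check rest wholly on assumed shifts and should not be cited as the effect of this instruction. The conclusion assumes the usual meaning of single-blind (participant blinded) and that no concealment step is described in text lost from the available copy.

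**What to change.** - **5.2.1.c:** replace the wattage on the Nurses Flow Sheet with a participant-specific arm code. Keep the code-to-wattage key on a separate set-up card held by whoever sets the device.
- **5.3.1:** state that the participant is the blinded party.
- **2.4.2:** state that the Assignment Tracking Log entry is made out of the participant's sight.
- **Video topography (5.4.1 to 5.4.3):** give coders files labelled only by Study ID and arm number, without access to the log. The sequence table printed in 2.4.2 would let anyone who knows a participant's orientation number turn arm number into wattage.

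The cost is one edited form, one card, a labelling rule and one more step at device set-up. No visits or staff are added. The person who sets the device, possibly the CRC, stays unblinded, and participants may still sense the power, so the gain is partial.
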